**NCT number: NCT06187909**

**Document date: 11/2023**

## What is already known on this subject? What does this study add?

Modified Radical Mastectomy (MRM) is a surgical procedure that removes the entire breast, including the skin, breast tissue, areola, and nipple, along with most of the axillary lymph nodes. However, most of the chest muscles are left intact. It is a less invasive surgery than a radical mastectomy, which also removes the chest muscles. It is a standard option for treating breast cancer that has spread to the axillary lymph nodes.

Postoperative pain in MRM is a common problem that can affect the quality of life and recovery of patients. Some factors that can influence the pain intensity are:

- The extent of the surgery and the involvement of the axillary lymph nodes.
- The type and dose of anesthesia used during the surgery.
- The use of regional blocks or multimodal analgesia to reduce opioid consumption and side effects

Postoperative pain management is becoming an integral part of anesthesia care. Optimal pain control in patients undergoing MRM is imperative for good rehabilitation and functional outcomes. Current modalities in use aim to reduce postoperative opioid consumption to control postoperative pain thus minimizing its side effects in what is recently known as multimodal analgesia techniques.

Regional blocks have been introduced for postoperative pain relief such as thoracic paravertebral block (TPVB), thoracic epidural block (TEB), and intercostal blocks. The use of ultrasound guidance has much improved the success rate of the nerve blocks and the development of new techniques. Newer pain control modalities have been used providing adequate pain relief, not affecting muscle strength and utilized as excellent solutions for multimodal analgesia peri-operatively. Examples of these modalities are serratus anterior plane (SAP) block, pectoral nerve (PECS) block, and midpoint transverse process to pleura (MTP) block.

In this study we will compare the analgesic efficacies of modified pectoral plane (PECS II) block versus midpoint transverse process to pleura (MTP) block after MRM surgery.

## **1. INTRODUCTION / REVIEW:**

Breast cancer (BC) is the most commonly diagnosed cancer worldwide, with estimated new cases exceeding 2 million in 2020. Furthermore, it represents the leading cause of cancer death in women, with more than 680,000 deaths.

It is the most common type of female cancer in Egypt with an age-specific incidence rate of 48.8/100,000. Although incidence rate in Egypt is lower than the global figures, mortality is higher at an age-standardized rate of 20.4/100,000 compared with the US rate of 12.3/100,000 and the developed countries' rate of 12.8/100,000.

During Modified radical mastectomy (MRM), some of the nerves in the chest are severed. Most women have some level of pain in the days after the procedure. Severe acute postoperative pain following breast surgery not only increases the risk of persistent pain and affects recovery, it also leads to longer hospitalization and increased healthcare costs. Acute postoperative pain is an independent risk factor in the development of chronic post-mastectomy pain.

Multimodal techniques for pain management have been recommended by The American Society of Anesthesiologists (ASA) for the management of acute postoperative pain. These techniques include regional analgesia, intravenous (IV) and oral analgesics as opioids, paracetamol and nonsteroidal anti-inflammatory drugs (NSAIDs). Inappropriate postoperative analgesia may increase morbidity and mortality.

PECS-II is an interfascial plane block in which local anesthetic is injected between the pectoralis and serratus anterior muscles that blocks the long thoracic nerve as well as the pectoral, intercostobrachial, and inter-costal III, IV, V, and VI nerves. PECS-II is a less invasive and easier to perform alternative to thoracic paravertebral block (TPVB). This block, defined by Blanco et al., provides adequate and safe post-operative analgesia in the anterior chest wall after breast surgery. The most common complications are pneumothorax, infection, local anesthetic systemic toxicity (LAST) / allergy, vascular puncture, and failed block.

The MTP block was first described as a modified paravertebral block in 2017. The local anesthetic (LA) is administered between the transverse process and the pleura. This results in a LA spread to the dorsal and ventral rami in the paravertebral space through the fenestrations in the superior costotransverse ligament (SCTL) at the level of injection, and frequently to adjacent levels. The advantage of this novel technique is that it does not require identification

of the SCTL and the injection point, which is midway between the pleura and transverse process, which makes this approach much safer than the conventional TPVB approach since the needle is farther from the vital structures like pleura, nerves, and vasculature. This technique is used for pain relief after mastectomy, thoracic, abdominal, and spinal surgery and was found effective due to its simplicity and lower risks compared to epidural analgesia.

However, no study exists in the literature that compares these blocks in modified radical mastectomy.

## **2. AIM / OBJECTIVES:**

This study aims to compare the analgesic efficacies of the modified pectoral plane block (PECS II) and the midpoint transverse process to pleura block (MTP), after modified radical mastectomy (MRM) surgery.

## **3. METHODOLOGY: Patients and Methods**

### **- Study Design and Ethics**

This will be a single-center, prospective, randomized, comparative study. Approval will be obtained from the Medical Research Ethical Committee of the Faculty of Medicine, Ain Shams University (FMASU MD311/2023). The trial will be registered at ClinicalTrials.gov (NCT06187909). Written informed consent will be obtained from all participants.

### **- Sample Size Calculation**

The sample size was calculated using G\*Power version 3.1.9.7 (Heinrich Heine University, Düsseldorf, Germany). The PECS II and MTP groups' mean postoperative pain scores were compared using a two-tailed independent-samples t-test. A minimum of 44 patients per group were needed based on an assumed effect size (Cohen's d) of 0.7, which was obtained from expected clinically relevant differences in VAS pain scores after 4 hours postoperatively, a power of 90% ( $1-\beta = 0.90$ ), and a two-sided alpha level of 0.05. Pilot observations and existing clinical evidence suggesting that intergroup variations in analgesic efficacy are most noticeable in the early postoperative period served as the basis for the effect size estimate.

### **- Participants**

Eighty-eight adult female patients, aged 40 to 65 years, ASA physical status I-II, scheduled for elective modified radical mastectomy will be enrolled.

**Exclusion criteria will include:** allergy to local anesthetics, coagulopathy, infection at the injection site, refusal to participate, or inability to understand the pain scale.

### **- Randomization and Blinding**

Patients will be randomly assigned to one of two groups using computer-generated random numbers sealed in opaque envelopes:

- 1- Group PECS (n = 44): Ultrasound-guided PECS II block.
- 2- Group MTP (n = 44): Ultrasound-guided MTP block.

Patients will be sedated during block placement. Due to the distinct anatomical sites, full patient blinding will not be possible. Outcome assessors collecting postoperative data will be blinded to group allocation. The anesthesiologists performing the blocks will not participate in data collection.

### **- Interventions**

All blocks will be performed preoperatively under standard monitoring and mild sedation with intravenous midazolam (0.025 mg/kg). A high-frequency linear ultrasound probe and a 22-gauge, 80-mm echogenic needle will be used under aseptic precautions.

PECS II block: In the supine position, 10 mL of 0.25% bupivacaine will be injected between the pectoralis major and minor muscles. The probe will then be repositioned laterally and 10 mL will be injected between the pectoralis minor and serratus anterior muscles at the level of the third to fourth ribs.

MTP block: With the patient seated, the probe will be placed parasagittally about 3 cm lateral to the midline at the T2 and T6 vertebral levels. A 22-gauge needle will be advanced in-plane to the midpoint between the transverse process and pleura, and 10 mL of 0.25% bupivacaine will be injected at each level.

### **- General Anesthesia**

All patients will receive standardized general anesthesia. Induction will be with intravenous propofol 2 mg/kg, fentanyl 2  $\mu$ g/kg, and atracurium 0.5 mg/kg. Anesthesia will be maintained with isoflurane (1.2–1.5 MAC) in 50% oxygen–air. Additional atracurium will be administered as required. Ventilation will be adjusted to maintain normocapnia. Neuromuscular blockade will be reversed with neostigmine 0.05 mg/kg and atropine 0.02 mg/kg. Extubation will be performed once standard criteria are met.

### **- Outcome Measures**

**Primary Outcome:** Pain intensity at rest was assessed by a 10-cm Visual Analogue Scale (VAS; 0 = no pain, 10 = worst pain imaginable) at 4 hours post-operatively.

#### **Secondary Outcomes:**

- 1- VAS scores on admission to the PACU and at 2, 8, 12, 18, and 24 hours post-operatively.
- 2- Time to first request for rescue analgesia.
- 3- Total 24-hour consumption of rescue analgesia (intravenous nalbuphine 5 mg bolus for VAS  $\geq 4$ ).

**4-** Incidence of block-related complications (hematoma, pneumothorax, local anesthetic systemic toxicity).

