**- Statistical Analysis**

Data will be coded, sorted, and analyzed using IBM SPSS Statistics version 28.0 (IBM Corp., Chicago, USA). Normality will be assessed with the Shapiro–Wilk test. Quantitative data will be expressed as mean  $\pm$  SD and compared using an independent t-test. Qualitative data will be expressed as numbers and percentages, analyzed with Chi-square or Fisher's exact test. The log-rank test will be used to compare the time to first rescue analgesia. A p-value  $< 0.05$  will be considered statistically significant.

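### Do the six secondary VAS times need a multiplicity rule or a statement on how to read them?

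*Combined protocol and SAP*

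**What the plan says.** Under Outcome Measures there is one primary outcome at one time: "Pain intensity at rest was assessed by a 10-cm Visual Analogue Scale", taken 4 hours after surgery. Under Secondary Outcomes, item 1 is "VAS scores on admission to the PACU and at 2, 8, 12, 18, and 24 hours post-operatively", which is six further times. The other items are time until rescue is first requested, 24-hour nalbuphine use and block complications.

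The Sample Size Calculation rests on the 4-hour score, with "a two-sided alpha level of 0.05", 90% power and a standardised difference of 0.7. It adds the expectation that "intergroup variations in analgesic efficacy are most noticeable in the early postoperative period".

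In Statistical Analysis, quantitative data are summarised as mean and "SD and compared using an independent t-test", and a p-value below 0.05 "will be considered statistically significant". That sentence is not limited to any outcome. The section describes no multiplicity adjustment, testing order, repeated-measures model or overall pain summary, and does not call the secondary results supportive. The Aim / Objectives section speaks of comparing analgesic efficacy and names no time.

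**The concern.** Only one method is given for quantitative data, so the natural reading is a separate t-test at 0.05 for each of the six secondary times. A significant result at, say, 12 hours would carry the same label as a significant result at 4 hours. If 4 hours were null and another time were not, someone could point to the broadly worded aim and claim that the blocks differ. If 4 hours were significant, a chance finding between 8 and 24 hours could be taken for a lasting difference. At stake is a false statement about relative efficacy resting on a secondary time. The error rate of the primary test is not in question.

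**Working it through.** **Inputs.** From the Sample Size Calculation: d = 0.7, two-sided alpha 0.05, power 90%, 44 per group. From Outcome Measures and Secondary Outcomes: one primary time and six secondary VAS times. The documents give no correlation between VAS times, so it is assumed and varied.

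**1. The plan's own figure.** Normal approximation: n = 2(1.960 + 1.282)²/0.7² = 42.9, so 43 per group. Exact noncentral t: at 44 per group the noncentrality is 0.7 × √(44/2) = 3.283 on 86 df, giving power 0.901; at 43 per group power is 0.894. The stated 44 reproduces.

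**2. Independence limit, no difference at any time.** At least one of six significant: 1 − 0.95⁶ = 0.265. Non-significant 4-hour result together with at least one significant secondary time: 0.95 × 0.265 = 0.252.

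**3. Correlated times, no difference at any time.** Let all seven test statistics share a common correlation ρ, and let a(u) be the chance that one statistic lies within ±1.96 given the shared normal component u. Then P(at least one of six) = 1 − E[a⁶], and P(4 hours null and at least one of six) = E[a] − E[a⁷].

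| Assumed ρ | At least one of six | 4 h null and at least one of six |
|---|---|---|
| 0 | 26.5% | 25.2% |
| 0.5 | 20.7% | 18.0% |
| 0.7 | 16.4% | 12.8% |
| 0.9 | 10.8% | 6.4% |
| 0.95 | 8.9% | 4.2% |

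Simulated t-tests with 44 per arm agree: 25.0%, 18.1%, 13.2% and 6.3% for the last column at ρ = 0, 0.5, 0.7 and 0.9. If correlation instead decays with time, at 0.5, 0.7 or 0.9 per 4 hours, that column becomes 21.0%, 17.1% or 9.9%.

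**4. Under the plan's design assumption.** With d = 0.7 at 4 hours, the primary is non-significant with probability 1 − 0.901 = 0.099. A null primary with a significant secondary time therefore cannot occur in more than about 10% of trials, whatever the correlation.

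**5. Early-only effect.** Assume d = 0.7 at PACU, 2 and 4 hours and no difference afterwards. At least one of 8, 12, 18 and 24 hours is then falsely significant in 19%, 16% or 10% of trials at ρ = 0, 0.5 or 0.9. The independence value is 1 − 0.95⁴ = 0.185.

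**6. What a remedy would change.**
- *Labelling the times supportive and giving 95% intervals.* The half-width is 1.988 × √(2/44) = 0.424 SD. Such an interval excludes zero exactly when the t-test gives p < 0.05, so the rates in step 3 are unchanged.
- *Holm across the six times.* The strictest step is 0.05/6 = 0.0083. Power at one secondary time with d = 0.7 falls from 0.901 to 0.719. Without a gate on the 4-hour result, the chance of any false VAS claim, primary included, is still 9.6%, 8.2% or 5.3% at ρ = 0, 0.5 or 0.9. With the gate it is held at 5%.

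**The case for a change.** The strongest case for a change is that the silence is real and cheap to fill. The ranking of outcomes implies how a lone secondary result should be read, but no sentence says so, and one threshold sentence covers every outcome. The plan itself expects differences mainly early, so a chance result at a late time is realistic even when the primary succeeds (10% to 19% in step 5). A rule written after the data are seen carries less weight than one written before, and two sentences would cost no patients and no primary power.

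The facts in this argument stand; the conclusion does not follow. Naming one primary outcome at one time and sizing the trial on it is how a plan states which result answers its aim, and a short aim need not repeat the time. The threshold sentence defines a label. It sets no success rule and does not let a secondary time stand in for the primary. The percentages are thus frequencies of a pattern, and the pattern misleads only if an author claims efficacy against the plan's own ranking. The t-test sentence in the Sample Size Calculation, "mean postoperative pain scores were compared using a two-tailed independent-samples t-test", belongs to the 4-hour calculation and does not settle how the other times are analysed. The six-test reading comes only by default from the Statistical Analysis section.

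**Conclusion.** No change is needed. The missing interpretive sentence is a gap that an analyst fills correctly from the outcome ranking: 4 hours decides, and the other times describe the course of pain. Writing that down for the six VAS times would be harmless, but it would alter no test, estimate or interval. Formal adjustment is a trade-off on which reasonable statisticians differ. Leaving secondary outcomes unadjusted beneath a single primary is a common choice, and Holm would give up 18 percentage points of power at its strictest step (90% to 72%).

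The size of the point is an 11% to 21% chance of at least one nominally significant secondary VAS time when the blocks are equally effective throughout. This assumes six separate t-tests and a common correlation of 0.9 to 0.5; 26% requires scores from the same patient within 24 hours to be independent. The 4-hour test keeps its 5% error in every case. The conclusion would differ if the plan allowed an efficacy claim from any one of the times, and it does not.

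### Secondary outcome 4 names three block-related complications and leaves out vascular puncture and allergic reaction, which the Introduction ranks among the most common with PECS II; nobody is clearly assigned to record events at the block

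*Combined protocol and SAP*

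**What the plan says.** Item 4 under Secondary Outcomes reads "Incidence of block-related complications (hematoma, pneumothorax, local anesthetic systemic toxicity". It contains no word such as ‘including’ and gives no observation period. Item 1 follows VAS to 24 hours and item 3 totals rescue analgesia over 24 hours.

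The Introduction says of PECS II: "The most common complications are pneumothorax, infection, local anesthetic systemic toxicity (LAST) / allergy, vascular puncture, and failed block". Vascular puncture is mentioned nowhere else. Allergy to local anesthetics appears otherwise only under Participants, among the reasons for exclusion: "allergy to local anesthetics, coagulopathy, infection at the injection site, refusal to participate, or inability to understand the pain scale".

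On timing and personnel, the Interventions section states "All blocks will be performed preoperatively under standard monitoring and mild sedation", and Randomization and Blinding states "Outcome assessors collecting postoperative data will be blinded to group allocation. The anesthesiologists performing the blocks will not participate in data collection". Under Statistical Analysis, categorical outcomes are handled as follows: "Qualitative data will be expressed as numbers and percentages, analyzed with Chi-square or Fisher's exact test".

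**The concern.** The outcome carries the general label of block-related complications, but its content is narrower than the protocol's own account of what commonly goes wrong with one of its two blocks. Two of the omitted events, vascular puncture and allergic reaction, can arise at or soon after the injection. If only the three named events are counted, the trial could report no complications in an arm where punctures or reactions had occurred.

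A second gap concerns the recorder. The blocks precede surgery, the blinded assessors gather postoperative data, and the operators are kept out of data collection without qualification. Taken literally, no one is charged with noting what happens at the needle. That affects a named event too, namely LAST with early onset. Without an observation window, it is also unclear whether item 4 begins at needle insertion or after the operation.

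What is at stake is the completeness of one secondary safety outcome, not the efficacy result.

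**Working it through.** **Step 1. The two lists side by side.**

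| Event | Introduction (PECS II) | Secondary outcome 4 |
|---|---|---|
| Pneumothorax | yes | yes |
| LAST | yes | yes |
| Allergy | yes | no |
| Vascular puncture | yes | no |
| Infection | yes | no |
| Failed block | yes | no |
| Hematoma | no | yes |

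Four events from the Introduction are absent from item 4. The sections on blinding, interventions, general anesthesia and statistical analysis contain no general adverse-event recording that would pick them up.

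**Step 2. What item 4 catches indirectly.** A puncture followed by hematoma is counted, and so is one followed by LAST. The uncounted remainder is a puncture with neither consequence. The allergy exclusion can act only on known allergy, so it lowers the expected number of reactions but records none.

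**Step 3. Size under assumed rates.** The documents give no complication rate, so there is no figure of the plan's to reproduce here. Let r be the assumed proportion of patients with an uncounted event (puncture without hematoma or LAST, or an allergic reaction). The number of patients is 88, from the Participants section. Expected events = 88 × r; chance of at least one = 1 − (1 − r)^88.

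| r (assumed) | Expected uncounted events | Chance of at least one |
|---|---|---|
| 0.5% | 0.44 | 36% |
| 1% | 0.88 | 59% |
| 2% | 1.76 | 83% |
| 5% | 4.4 | 99% |

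**Step 4. What an omission does to one arm (hypothetical).** Suppose two punctures in an arm of 44 are not counted. The true figure is 2/44 = 4.5%, exact (Clopper–Pearson) 95% interval 0.6% to 15.5%. The reported figure would be 0/44, interval 0% to 8.0%, the upper limit being 1 − 0.025^(1/44) = 0.0804.

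**Step 5. What the planned test can show.** With 44 per arm and k events against none, the two-sided Fisher p-value is 2 × C(44,k)/C(88,k). For k = 5, p = 0.055; for k = 6, p = 0.026. At least six events against none are needed to reach p < 0.05, so the added items can serve description only.

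**Step 6. The primary design.** The sample size rests on VAS at 4 hours with d = 0.7, 90% power and two-sided alpha 0.05. The exact t-test calculation gives 43.87, rounded up to the stated 44 per group. Nothing in item 4 enters it.

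**The case against.** The strongest reply is that the Introduction is background on one block and does not define an outcome. A sponsor may choose a short list of consequential harms, particularly when the stated aim is analgesic efficacy. If item 4 means exactly three events, their incidence will be reported correctly; if the parenthesis gives examples, nothing is excluded. This is fair as far as it goes: understatement is relative to the Introduction's list. But the text does not say which reading is meant. The first omits events the protocol itself calls common, and the second leaves the outcome without a fixed definition, so either needs an edit.

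The operator bar follows directly on a sentence about postoperative data and probably concerns only that. A reader might infer that operators are forbidden to report events at the block; the wording permits that reading but does not establish it. What stands is that no recorder is named.

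The allergy item has a real difficulty. General anesthesia gives every patient propofol, fentanyl, atracurium and isoflurane after the block, so a reaction may not be due to the local anesthetic. Without an attribution rule, the new item could add events unrelated to the block.

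A reader might also infer that the trial is losing the chance to test the vascular-safety argument for MTP, "since the needle is farther from the vital structures like pleura, nerves, and vasculature". The documents do not support that. The comparison there is with the conventional thoracic paravertebral block (TPVB), which is not an arm of this trial, so no amount of puncture recording could test it.

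Finally, the rates in the working are assumed, and they pool two different events. They show what could go uncounted, not what will.

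**Conclusion.** The point holds as a modest, inexpensive improvement. Read as a closed list, item 4 omits vascular puncture and allergic reaction, and the plan records neither elsewhere after the block. Under assumed rates of 0.5% to 5%, between 0.44 and 4.4 such events would be missed on average in 88 patients. That range rests wholly on the assumption, and on these events causing none of the three named complications.

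The recording gap is a matter of unclear wording. It deserves a sentence because it touches early LAST as well as the omitted events.

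A reader might go further and take it that every puncture without hematoma is lost, or that the efficacy result is compromised. Neither follows: a puncture leading to LAST is counted, and the 4-hour VAS comparison and the sample size do not depend on item 4.

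**What to change.** 1. Add vascular puncture and allergic reaction to item 4, each defined before enrolment in the same words for both arms. For allergic reaction, state the rule by which it is attributed to the block rather than to the general anesthetic drugs.
2. State an observation window for item 4, for example from needle insertion to 24 hours, which is the last VAS time point.
3. In Randomization and Blinding, say that block operators complete a short procedure form on events at the block, that the form is withheld from the blinded assessors, and that operators collect no postoperative data.
4. Report each event as a count by arm, descriptively. Exact 95% intervals are a useful option.

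Infection should be added only if follow-up is long enough to detect it. Block failure could be recorded as an optional descriptive item, kept apart from harms, but it needs a definition that the documents do not supply.

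The cost is one short form, a clarifying sentence on blinding, a window and definitions in item 4, and one line in Statistical Analysis. There are two downsides. Operator-reported events are unblinded, and the reported complication rate may look higher than with the three-event list.

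### Block-related hematoma is not comparable between the arms, because a postoperative chest-wall or axillary hematoma is a plausible block event only after PECS II

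*Combined protocol and SAP*

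**What the plan says.** Under Secondary Outcomes, item 4 reads "Incidence of block-related complications (hematoma, pneumothorax, local anesthetic systemic toxicity". The protocol does not define a hematoma, say where or when to look for one, or say who decides that it came from the block.

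The Interventions section sets the needle sites.
- PECS II, first injection: "10 mL of 0.25% bupivacaine will be injected between the pectoralis major and minor muscles".
- PECS II, second injection: "10 mL will be injected between the pectoralis minor and serratus anterior muscles at the level of the third to fourth ribs".
- MTP: "the probe will be placed parasagittally about 3 cm lateral to the midline at the T2 and T6 vertebral levels".

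On timing, "All blocks will be performed preoperatively under standard monitoring and mild sedation".

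The opening background section says that the operation "removes the entire breast, including the skin, breast tissue, areola, and nipple, along with most of the axillary lymph nodes", while "most of the chest muscles are left intact".

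Randomization and Blinding states that those who collect postoperative data will not know the allocation, and that those who perform the blocks will stay out of data collection. It mentions the different block sites only as a reason why patients cannot be fully blinded. Statistical Analysis gives one general rule for qualitative data, chi-square or Fisher's exact test, and names no test for hematoma specifically.

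**The concern.** The outcome counts a hematoma only if it is judged to come from the block, and that judgement is not equally hard in the two arms. Both blocks precede surgery. After PECS II, a hematoma on the chest wall or in the axilla has two candidate causes, the needle and the operation. After MTP, the same hematoma has one, because the needle went into the back.

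If site is the criterion, a surgical hematoma can count as an event in one arm only. Randomisation balances surgical bleeding between the arms, but it does not balance whether that bleeding is eligible to be counted. A recorder who credits every chest hematoma to surgery makes the opposite error: true PECS II hematomas disappear, while MTP hematomas on the back remain visible.

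At stake is the reported hematoma incidence, one of three named components of the safety outcome. With 44 patients per arm, one or two misattributed events could make up the whole apparent difference.

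**Working it through.** **1. The plan's own figure.** Sample Size Calculation gives 44 per group for a two-sided t-test with d = 0.7, alpha 0.05 and power 90%. The noncentral-t solution is 43.87, which rounds up to 44; power at 44 per group is 90.1%. The figure reproduces. It concerns the 4-hour VAS and has no bearing on hematoma.

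**2. Where the needle and the surgery meet.** The overlap is an inference from two sections and is not stated in the protocol.

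| | PECS II | MTP |
|---|---|---|
| Injection site (Interventions) | pectoral and serratus planes, second injection at ribs 3–4 | beside the spine, T2 and T6 |
| Relation to breast and axillary dissection (background section) | beneath or beside it | away from it |
| Possible causes of a postoperative chest or axillary hematoma | block or surgery | surgery |
| Possible causes of a hematoma at the back punctures | not applicable | block |

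**3. Attribution by site, all chest hematomas charged to the block.** The documents give no hematoma rate, so the surgical rate s is assumed to be 2%, 5% or 10%. True block hematoma is set to zero in both arms, n = 44 per arm, and the MTP count is 0.

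- Expected spurious PECS II events = 44 × s.
- Chance of at least one = 1 − (1 − s)^44.
- Two-sided Fisher p for k against 0 = 2 × C(44,k)/C(88,k). For k = 5, p = 0.055; for k = 6, p = 0.026. Six events are therefore needed.
- Chance of false significance = P(Bin(44, s) ≥ 6).

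| Assumed s | Expected spurious events | At least one | Fisher p < 0.05 |
|---|---|---|---|
| 2% | 0.9 | 59% | 0.02% |
| 5% | 2.2 | 90% | 2.2% |
| 10% | 4.4 | 99% | 27% |

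If only half are charged to the block, s is replaced by s/2. Expected events become 0.4, 1.1 and 2.2, and the chance of at least one becomes 36%, 67% and 90%. The chance of Fisher p < 0.05 is then at most 2.2%.

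**4. Attribution by site, all chest hematomas credited to surgery.** A true PECS II rate of 5% (assumed) means 44 × 0.05 = 2.2 expected events, reported as 0.

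**5. A truly blinded assessor who counts every hematoma alike.** With true block rates b1 and b2, and surgical bleeding independent of the block, the observed rate in each arm is 1 − (1 − b)(1 − s). The expected difference is (1 − s)(b1 − b2): its sign is preserved and it shrinks slightly. For s = 5%, b1 = 2% and b2 = 1%, the observed rates are 1 − 0.98 × 0.95 = 6.90% and 1 − 0.99 × 0.95 = 5.95%. The difference moves from 1.00 to 0.95 percentage points, and the ratio falls from 2 to 6.90/5.95 = 1.16. That is dilution, without a directional bias between arms.

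**The case against.** The strongest reply is the blinding. A directional bias needs a recorder who treats the same chest hematoma differently by arm, and the protocol says the postoperative assessors will not know the arm. If that holds, surgical hematomas are counted or excluded alike and randomisation balances them. This stands. A reader might infer that the comparison is certainly biased, or biased against PECS II; the documents support neither. What blinding does not settle is how such an assessor is to decide that a hematoma is block-related: judging by injection site requires knowing which block was given. The plan leaves this open.

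The anatomy can also be pushed too far. Both PECS II injections lie between muscles that are mostly preserved, beneath the removed breast. A reader might infer that a PECS II hematoma can never be told apart from a surgical one. The documents show closeness to the dissection, which makes attribution harder, and no more than that.

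The rates of 2% to 10% and the full attribution to one arm are assumptions, and the between-arm test comes only from the general rule for qualitative data. A reader might infer that a false safety signal is likely. Even with full attribution it reaches 27% only at the highest assumed rate, and it is about 2% or less otherwise.

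Finally, hematoma is one component of the last-listed secondary outcome. That limits the importance of the point but does not answer it.

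**Conclusion.** The point holds in a conditional form. As worded, the outcome requires an attribution that is not equivalent in the two arms, and the plan does not say how to make it. Attribution by site biases the reported incidence by arm, upward or downward for PECS II according to the recorder's habit. Genuinely blinded counting of all hematomas gives a diluted comparison, which is no longer a measure of block-related events.

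The size cannot be fixed from the documents. About 1 to 4 spurious events in 44 would be expected under full attribution to PECS II, with half that under half attribution. The damage falls mainly on the reported incidence and seldom on the significance test. The primary outcome, the sample size and the other secondary outcomes are untouched. The conclusion rests on the field overlap inferred from the background and Interventions sections, and on the absence of any attribution rule. It is a modest defect, worth correcting because the remedy is nearly free.

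**What to change.** Reword the hematoma part of item 4 as follows.

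1. The blinded assessor records every hematoma through 24 hours, in both arms, by site (chest wall or axilla; back), without attributing a cause.
2. Any hematoma, at any site, is compared by randomised arm, with exact confidence intervals. This needs no causal judgement and is protected by randomisation. The interval matters because counts will be small: 0 of 44 still has a two-sided 95% upper limit of 1 − 0.025^(1/44) = 8.0%.
3. Block-related hematoma is reported only as a descriptive sub-count, with a note that attribution is not comparable between the arms.

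The cost is one or two data fields. The downside is that surgical hematomas dilute the total, as step 5 of the working shows. Looking at the back may also reveal puncture marks and hence the arm, so the scheduled inspection is best made after the 24-hour VAS has been recorded.

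An alternative is to count only hematomas seen at the injection site before incision. It would miss late block bleeds. It would also naturally fall to the person holding the probe, whom the protocol keeps out of data collection. Recording by site in both arms avoids both problems.
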